# **Frequency of vascular events using “short treatment” thrombosis prophylaxis in fast-track hip and knee arthroplasty (FETA-study)**

A prospective descriptive cohort study using prophylaxis for  $3\pm2$  days in patients receiving fast-track elective hip or knee arthroplasty

In cooperation with the Lundbeck Foundation Centre for Fast-track Hip and Knee Replacement(LCFHK).

## **Background:**

Surgery is recognized as being related to the development of thrombosis, especially after major orthopedic surgery (1;2). These complications are defined as venous thromboembolic events (VTE), including deep venous thrombosis (DVT) and pulmonary embolism (PE).

Pharmacological prophylaxis reduces the risk of thrombosis and recommendations (grade 1a) from the American College of Chest Physicians (ACCP) are one of three following anticoagulantia:

1: Low molecular weight heparin (LMWH)

2: Faktor Xa-inhibitors

3: Vitamin-K-antagonists

Recommended duration of thrombosis prophylaxis is 10 days after total knee arthroplasty (TKA) and 35 days after total hip arthroplasty (THA) (3).

In the United States of America most surgeons follow ACCP guidelines. Studies have shown that about 90 % of surgeons adhere to guidelines, however, many use additional prophylaxis such as compressive stockings(4). More recent investigations find a lower compliance amongst surgeons world wide of about 50% (5). There are disagreements about the validity of the before mentioned guidelines due to the many exclusion and inclusion criteria in the analyzed studies and due to the fact that it is the thoracic surgeons who dictate the orthopedic surgeons guidelines(6), therefore the American Academy of Orthopedic Surgeons (AAOS) has developed their own guidelines. The main difference between ACCP and AAOS guidelines is the use of compressive stocking and acetylsalicylic acid as only prophylaxis in patients at risk of bleeding and a general disagreement on the relationship of DVT and PE(7).

In Denmark, the Danish Society of Orthopedic Surgeons (DSOS) has their own guidelines of 7 days of postoperative thrombosis prophylaxis which illustrates the controversies in this area.

The few studies who do not comply with ACCP guidelines, using acetylsalicylic acid (and early mobilization) as only prophylaxis show very low frequencies of vascular events (8-11), raising doubts about the best choice of treatment, especially considering increased mortality with LMWH compared to acetylsalicylic acid(12).

Preliminary uncontrolled studies in TKA have shown that early mobilization (<24 hours after surgery) reduces risk of postoperative VTE in patients treated with LMWH(13), and as frequency of DVT following TKA is decreasing over time using warfarin (VKA) as prophylaxis(14), interest in postoperative mobilization is increasing.

The trend towards enhanced recovery protocols (fast-track surgery) where optimized pain treatment, early mobilization (<24 hours), preoperative patient information etc. aims to decrease length of hospital stay. Data on THA and TKA patients from Hvidovre Hospital proves that 92 % of patients were discharged within 5 days and 41 % within 3days(15).

An un-published preliminary study from Hvidovre Hospital in about 2000 patients shows very low frequency of symptomatic VTE in 90-days follow-up, with mortality of 0.15%, DVT/PE/death in TKA of 0.66%

and 0.52% in THA when using a fast-track setup (16). This is lower than comparable literature with thrombosis prophylaxis for 35 days postoperatively.

A group of experts has suggested that pharmacological thrombosis prophylaxis in patients with early mobilization is non-obligatory, this would result in decreased side-effects such as bleedings, less inconvenience in the patients and economical advantages(17). This has resulted in short prophylaxis treatment being standard of care in several departments in Denmark (i.e. Hørsholm, Hvidovre and Farsø hospitals).

No previous study has been published with a detailed description on the risk of vascular events, including arterial complications, using short-treatment thrombosis prophylaxis in a fast-track setup after THA/TKA or commented on identification of risk factors(2;18;19).

It must be mentioned that Asian patients (Korea, China etc.) do not have a tradition for thrombosis prophylaxis after THA due to the low frequencies of VTE without prophylaxis. In this context, differences in genetics and dietary habits etc. must be considered (20;21).

## **1. Intention of study**

### **1.1 Primary outcome**

To conduct a high quality cohort study to investigate the frequency of symptomatic DVT, PE, acute myocardial infarction (AMI), stroke and other vascular events and/or death of other causes in patients having elective uni and bilateral THA/TKA, revision THA/TKA and uni-KA in a fast-track setup including short treatment thrombosis prophylaxis( $3 \pm 2$  days). Additionally, identification of risk factors for such events will be attempted (Appendix 4).

### **1.2 Hypothesis**

No increased frequency of symptomatic thromboembolic events in THA/TKA in a fast-track setup with short treatment thrombosis prophylaxis.

## **2. Participants and methods**

### **2.1 Design**

A detailed prospective multicenter high quality cohort study of about 5000 patients  $> 18$  years old, having elective uni- or bilateral THA/TKA, revision and uni-KA with thrombosis prophylaxis only during hospitalization ( $3 \pm 2$  days/  $72 \pm 48$  hours). Follow-up is 90 days. Patients with postoperative clinical

symptoms of vascular events are encouraged to seek a physician in order to receive relevant examination and treatment (se appendix 3).

### 3. Patient selection

[figure not shown]
Patients will be included from the Orthopedic departments of: Århus Sygehus, [name], Regionshospitalet Holstebro, Hvidovre Hospital, Sydvestjysk sygehus Grindsted, Vejle Hospital and Ortopædkirurgien Nordjylland (Farsø), starting ultimo December '09 til December '11, 5000 patients need to be included. In all centers mean length of hospital stay (LOS) is short, with discharge before day  $3 \pm 2$ . LOS is defined as number of nights spent in hospital after surgery.

#### 3.1 Inclusion criteria

- Males and females > 18 years old
- Primary uni/bilateral THA/TKA, revision THA/TKA and uni-KA in fast-track setup
- Discharge on day  $3 \pm 2$ /72 ± 48 hours

#### Observations and tests

#### 3.2 Plan:

#### Day -7 til -1:

The patient goes through physical examination and demographics are registered (appendix 4).

**Dag 0:** defined as day of surgery

Patient has surgery

Thrombosis prophylaxis according to local guidelines (appendix 1).

**Dag 3 ± 2:** Patient is discharged (4.3) and ceases thrombosis prophylaxis.

**Dag 90 ± 5:** End follow-up

### 3.3 Discharge criteria

- Independent in daily activities
- In/out of bed
- In/out of chair
- Independent walk with mobility aid

If the patient is not discharged on day 3 ± 2, the patient should follow Danish Society of Orthopedic Surgeons (DSOS) guidelines (7 days). This group will be followed separately.

In case of regular treatment with acetylsalicylic acid or other thrombocyte inhibitor, this should be continued after surgery and with addition of thrombosisprophylaxis during hospitalization.

If the patient is in regular potent anticoagulative therapy (PACT), the patient will need bridging, with cessation of PACT 4 days preoperatively, and postoperative thrombosis prophylaxis until the patient's INR reaches therapeutic values (INR 2-3). This is done by the patients' general practitioner.

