## 4. Statistics

A pre-study power-calculation showed that at least 3000 patients were needed (power( $\beta$ ) 82 % with a significance level ( $\alpha$ ) of 0,05) with expected event-rates of 3% (22-25) and a maximum event rate of 4 %. We expect to include about 5000 patients which would increase power and the statistic possibility of identifying risk-factors (preoperative variables). In addition isolated analysis on the primary procedures will be performed.

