## **8. Interim analysis**

An interim analysis will be done after 1500 and 3000 patients.

Intention: To evaluate whether the true risk of complications is higher (worse treatment) or lower (better treatment) 4%. Three analyses will be done. In each analysis, the risk of complication including CI will be calculated. In the 1st analysis (1500 patients), the exact 99.5% CI will be calculated, in the 2nd analysis an exact 99 % CI and in the 3rd analysis (5000 pt) an exact 95.2% CI.

In simulation, it has been calculated that if the true risk is 3%, the total power is 97.6%. If the true risk of events is 6%, total power is 99.9%.

In case of an unacceptable safety profile and/or a very high number of primary events, the Clinical event committee can recommend an early termination of the study to the Steering committee, who will decide hereafter.

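### Entry depends on discharge by day 5, but events count from the day of surgery and no population is named for the comparison with 4%

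*Combined protocol and SAP*

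**What the plan says.** - **Entry.** The third inclusion criterion in section 3.1 begins "Discharge on day" and gives 3±2, that is, days 1 to 5.
- **Late discharge.** Under section 3.3, patients not discharged by then follow the national society's prophylaxis guideline, and "This group will be followed separately". Section 19 item 8 corrects the durations in that guideline and says nothing about analysis.
- **Clock.** In section 3.2, day 0 is "defined as day of surgery", and follow-up ends on day 90±5.
- **Outcome.** Section 1.1 counts symptomatic DVT, PE, AMI and stroke, together with "other vascular events and/or death of other causes".
- **Exposure.** Section 2.1 describes a cohort "with thrombosis prophylaxis only during hospitalization".
- **Decision.** Section 4 plans on "expected event-rates of 3% (22-25) and a maximum event rate of 4"%. Section 8 gives the aim of the three analyses, at 1500, 3000 and 5000 patients, as "To evaluate whether the true risk of complications is higher (worse treatment) or lower (better treatment) 4"%. It does not say which patients these are.
- **Data.** Section 9 takes diagnosis codes, length of stay and death from the national register. Section 19 item 11 widens collection to all readmissions within 90 days.

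**The concern.** A patient who dies before discharge cannot meet the entry criterion. A patient whose PE on day 2 extends the stay past day 5 fails it because of the very event being counted. If the comparison with 4% uses patients who meet section 3.1, membership depends partly on the outcome, while the period at risk still starts at surgery.

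The 4% decides whether short prophylaxis is read as better or worse. Removing patients because they had an event lowers the observed rate. That makes a finding below 4% easier to reach and weakens the interim check for a rate above 4%. Section 8 keeps another safety route, since "the Clinical event committee can recommend an early termination of the study", but sets no figure for it.

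**Working it through.** **1. The plan's own figures.** An exact two-sided binomial test of 4% against a true 3%, with α = 0.05 and power of at least 82%, first reaches that power at n = 2838 (82.2%). This matches section 19 item 9. I then applied the section 8 rule: exact (Clopper-Pearson) intervals of 99.5%, 99% and 95.2% at 1500, 3000 and 5000 patients, with the first look that excludes 4% deciding.

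| Look | Below 4% | Above 4% |
|---|---|---|
| 1500 | ≤39 events | ≥83 events |
| 3000 | ≤92 | ≥149 |
| 5000 | ≤172 | ≥229 |

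Exact binomial recursion over the looks gives power of 96.8% at a true 3% (97.6% stated, by simulation) and above 99.9% at 6% (99.9% stated). At a true 4%, the chance of concluding below 4% is 2.4%. At a true 5%, the chance of concluding above 4% is 92%. The margin at the last look is one event: 172/5000 has an upper limit of 3.99%, and 173/5000 has 4.01%.

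**2. Outcome-dependent removal alone.** Let R be the 90-day risk in all operated patients and g the share of patients with an event who are removed because of it (in-hospital death, or an event that by itself delays discharge past day 5). Then

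observed rate = R(1 − g) / (1 − gR).

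For example, R = 4% and g = 5% give 0.04 × 0.95 / (1 − 0.002) = 3.81%. The patients removed beside 5000 retained number 5000 × 0.002 / 0.998 ≈ 10.

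*The one case with a figure in the documents.* The Background quotes 0.15% mortality in an unpublished 90-day series from one hospital. If all of it were in hospital, a true 4.00% would read (4.00 − 0.15) / (1 − 0.0015) = 3.86%. The chance of wrongly concluding below 4% becomes 7%. This covers deaths only, not non-fatal events that delay discharge.

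*Assumed shares.* The documents give no value for g.

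| g | True 4% reads | Concludes below 4% | True 5% reads | Concludes above 4% |
|---|---|---|---|---|
| 0 | 4.00% | 2.4% | 5.00% | 92% |
| 1% | 3.96% | 3% | 4.95% | 90% |
| 5% | 3.81% | 10% | 4.76% | 74% |
| 10% | 3.61% | 28% | 4.52% | 44% |

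At a true 5%, the chance of crossing the upper boundary at one of the two interim looks falls from 56% to 32% (g = 5%) or 14% (g = 10%).

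At the planned true 3%, concluding below 4% is correct. Its probability is 96.8% without removal and 99.3% or more for g of 5% or 10%, so nothing reverses.

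**3. Leaving out the whole late group.** Let q be the share discharged late and RR the ratio of late to early risk. The early-group rate is R / ((1 − q) + q·RR). The Background reports 92% discharged within 5 days at one hospital, so take q = 8%. With R = 4% and assumed ratios of 0.5, 1, 2 and 3, the early group shows 4.17%, 4.00%, 3.70% and 3.45%. The direction of the net effect therefore depends on a ratio that the documents do not give. A higher risk in late patients is plausible. Even then, part of the difference is a genuinely lower risk in short-stay patients, which is a change of target population and not pure error.

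**The case against.** The strongest reply is that sections 3.1 and 3.3 also fit one enrolled cohort split by length of stay. Late patients have a prophylaxis rule, later revised, and are followed; patients shut out of the study would need neither. Section 7 follows all included patients through the register. A reader might infer that the plan expressly excludes late patients from the 4% comparison, and the text does not go that far. What stands is that discharge day is written as an inclusion criterion and no section returns these patients to the comparison.

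A second reply is that short stay defines the exposure, so restricting to it is legitimate. That is right for a short-stay analysis. It does not justify counting from surgery in a group defined at discharge.

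Two other strong readings fail. One is that bias can only favour short treatment. This holds for outcome-dependent removal, but not for omitting the late group as a whole: with RR = 1 there is no net shift, and with RR = 0.5 the rate rises. The other is that index-stay events go uncollected because section 19 item 11 speaks of readmissions. The register extraction in section 9 is not limited to readmissions and includes death, so the data should exist. The gap is in how they are counted.

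**Conclusion.** The point holds as a gap that should be fixed. The population for the 4% comparison is not named, and the natural reading removes some patients because they had the outcome. That part of the selection lowers the rate. The net effect of omitting all late patients cannot be determined from the documents.

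The one case anchored in the documents is small: 4.00% reads 3.86%, and the false conclusion below 4% rises from 2.4% to 7%. The larger figures rest wholly on assumed shares of events. All of them assume 5000 patients in the main cohort and the section 8 rule applied as written. They matter when the true risk is near or above 4%. They do not show that the planned conclusion at 3% would be wrong, nor that selection of the assumed size occurs.

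**What to change.** **Main rate.** In sections 3.1, 3.3 and 8, drop discharge day as an entry condition for the 90-day rate and name the population. Suggested wording: *All eligible patients operated in the fast-track setup enter on day 0. Every primary event and death to day 90 counts, including the index stay, whatever the day of discharge. The interim and final comparisons with 4% use this population.* Report stays of up to 5 days and of more than 5 days beside the total.

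**Short-stay question.** Add a predefined landmark analysis from discharge to day 90, in patients discharged by day 5 without an earlier primary event, with its confidence interval. Discharge by day 5 does not by itself establish short prophylaxis, because Appendix 1 lists 7-day regimens at several sites, whereas sections 2.1 and 3.2 end prophylaxis with the hospital stay. These passages must be reconciled, and the landmark group should be described by prophylaxis actually received where data allow.

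**Cost.** Wording, an extra table, and chart review of index-stay events. Late patients are already followed, and the register supplies codes, length of stay and death. The price is a headline rate that may be higher and that answers a broader question than short treatment alone, since late patients follow a different prophylaxis rule. The split by stay and the landmark analysis help with this but do not fully isolate short treatment. Aligning the patient counts in section 8 with section 19 item 6 is a separate matter.

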## 4. Statistics

A pre-study power-calculation showed that at least 3000 patients were needed (power( $\beta$ ) 82 % with a significance level ( $\alpha$ ) of 0,05) with expected event-rates of 3% (22-25) and a maximum event rate of 4 %. We expect to include about 5000 patients which would increase power and the statistic possibility of identifying risk-factors (preoperative variables). In addition isolated analysis on the primary procedures will be performed.

## 5. Budget

The study is partly financed by Århus University (1.100.000dkr) and the Lundbeck Foundation Centre for Fast-track Hip and Knee Replacement(LCFHK) (550.000dkr). This has already been agreed upon.

Further project nurses/secretaries will be hired by LCFHK, therefore no further administrative assistance in relation to the project is expected.

There will be no pharmacological expenses.

Expenses in relation to transportation, travelling and course activities are expected to amount to about 50.000 dkr.

Data from the Danish National Patient Registry (NPR) about 15.000 dkr.

Other materials 5.000 dkr.

## **6. Safety analysis**

To evaluate the risk of bleeding-complications in patients having THA or TKA in a fast-track setup (Appendix 2).

## **7. Duration of study**

The expected duration of the study, assuming the aforementioned number of participants, is 24 months. All included patients will after  $90 \pm 5$  days be investigated by NPR. Duration of enrollment is estimated to be about 20 months. The study is expected to run from ultimo December '09 until December '11.

## **8. Interim analysis**

An interim analysis will be done after 1500 and 3000 patients.

Intention: To evaluate whether the true risk of complications is higher (worse treatment) or lower (better treatment) 4%. Three analyses will be done. In each analysis, the risk of complication including CI will be calculated. In the 1st analysis (1500 patients), the exact 99.5% CI will be calculated, in the 2nd analysis an exact 99 % CI and in the 3rd analysis (5000 pt) an exact 95.2% CI.

In simulation, it has been calculated that if the true risk is 3%, the total power is 97.6%. If the true risk of events is 6%, total power is 99.9%.

In case of an unacceptable safety profile and/or a very high number of primary events, the Clinical event committee can recommend an early termination of the study to the Steering committee, who will decide hereafter.

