## 17.5 Other thromboembolic events

Need to be defined by a relevant specialist.

## 18. Appendix 4

Date of surgery

Social security number

Joint (knee/hip)

Height: \_\_\_\_\_ cm

Weight: \_\_\_\_\_ kg

Hemoglobin level \_\_\_\_\_ mmol/l

(Taken no more than 1 week previously)

Patients' blood type?

Living conditions (alone, with spouse/others, in institution (nursing home etc.))

Smoking (yes/no)

Alcohol >2 units a day (yes/no)

Do you use walking aids prior to admission?

Are you feeling well rested in the morning?

Do you snore loudly?

Do you use compressive stockings regularly?

Do you receive treatment for high cholesterol (yes/no)

Do you receive treatment for high blood pressure (yes/no)

Do you have Type 1 diabetes (yes/no)

Do you have Type 2 diabetes (yes/no)

Have you had a previous cerebral attack?

Have you had a previous venous thromboembolic event?

Do you receive medication for any type of heart disease?

Do you receive medication for any type of pulmonary disease?

Do you receive medication for any type of psychiatric disease?

Do you have a family member who has had a deep venous thrombosis or pulmonary embolus?

Do you have a contraindication for antithrombotic medication?

Do you use antithrombotic medication regularly (marevan, acetyl salicylic acid etc)?

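### A complication risk below the 4% maximum is called better treatment, while hypothesis 1.2 has no reference rate, margin or conclusion rule, and item 9's sample size of 2076 does not follow from its stated inputs

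*Combined protocol and SAP*

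**What the plan says.** Section 8 plans analyses after 1500, 3000 and 5000 patients, with exact 99.5%, 99% and 95.2% confidence intervals. Their purpose is "To evaluate whether the true risk of complications is higher (worse treatment) or lower (better treatment) 4" per cent. It reports from simulation that "if the true risk is 3%, the total power is 97.6" per cent, and that power is 99.9% at a true 6%. Early termination may be recommended for an unacceptable safety profile or for "a very high number of primary events".

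Section 4 gives the same two rates another role: "expected event-rates of 3% (22-25) and a maximum event rate of 4" per cent. Here 4% is a ceiling and 3% is what the investigators expect.

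The hypothesis in Section 1.2 is "No increased frequency of symptomatic thromboembolic events in THA/TKA in a fast-track setup" with short prophylaxis. No comparator, reference rate or margin is stated. The primary outcome in Section 1.1 is wider: besides DVT, PE and AMI it takes in "stroke and other vascular events and/or death of other causes".

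The nearest text to a reference rate is Section 19, item 9. It gives 2838 patients for the Section 4 specification, using a two-tailed one-sample test against a constant. It then gives 2076 patients to detect a 1% increase in symptomatic VTE from a 1% baseline with 35 days of LMWH, at alpha 0.05 and 82% power.

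**The concern.** There are three linked problems.

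- **Label.** Calling a rate better because it lies below the maximum treats a ceiling as if it were a comparator's rate. There is no comparison arm, and nothing in the documents makes 4% the rate under longer prophylaxis.
- **Hypothesis 1.2.** The 4% comparison uses a broader endpoint than the hypothesis, and no section says which result would support or contradict 1.2. Item 9 supplies a detectable difference for sizing. Failing to detect a difference does not show that there is no increase.
- **Item 9.** Its VTE sample size disagrees with its own inputs, so the baseline that a reader would naturally take for 1.2 is itself in doubt.

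At stake is what may be concluded from a study that Section 13 expects to influence recommendations. A result that shows only a rate below a ceiling could be reported as superiority, or as confirmation of 1.2.

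**Working it through.** **Inputs.** Looks at 1500, 3000 and 5000 with two-sided alpha 0.005, 0.01 and 0.048 (Section 8); maximum 4% and expected 3% (Section 4); VTE baseline 1%, increase 1 point, alpha 0.05, power 82% (Section 19, item 9). Section 8 does not say which interval position gives which conclusion. I assumed that the interval must exclude 4% and that the endpoint is the primary composite.

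**1. Reproducing Section 8.** Exact limits for x events in n:

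- lower = Beta quantile(alpha/2; x, n − x + 1)
- upper = Beta quantile(1 − alpha/2; x + 1, n − x)

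The upper limit is below 4% at ≤39/1500, ≤92/3000 and ≤172/5000. The lower limit is above 4% at ≥83, ≥149 and ≥229. Summing exact binomial probabilities over the three looks, stopping at the first crossing:

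| True rate | Below 4% | Above 4% | Neither |
|---|---|---|---|
| 3.0% | 96.8% | 0.0% | 3.2% |
| 3.5% | 43.7% | 0.0% | 56.3% |
| 4.0% | 2.4% | 2.5% | 95.1% |
| 6.0% | 0.0% | >99.9% | 0.0% |

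The plan states 97.6% at 3% and 99.9% at 6%. The agreement is close enough to support the assumed rule.

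**2. What the label covers.** At the final look 172/5000 = 3.44%, with exact 95.2% limits 2.95% and 3.99%. The point estimate is above the expected 3% and the interval includes 3%, yet the result falls on the better side.

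**3. Item 9.** Exact two-sided one-sample binomial test, alpha 0.05, smallest N reaching 82% power:

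| Null | Alternative | N | Plan |
|---|---|---|---|
| 4% | 3% | 2838 | 2838 |
| 1% | 2% | 1143 | 2076 |
| 3% | 2% | 2076 | – |

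The first row matches exactly, so the method is the right one. For 1% against 2%, power at 2076 is 96.3%, not 82%. The printed 2076 fits a null of 3% with an alternative of 2%. The documents do not say which inputs were used.

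**4. Can the composite miss a doubling of VTE?** Let VTE rise from 1% to 2%. The documents do not give the non-VTE share, so I show a range and read the results from the table in step 1:

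- Non-VTE 2% (the plan's 3% − 1%): composite 4%; called better 2.4%, inconclusive 95%.
- Non-VTE 1.5% (assumed): composite 3.5%; called better 43.7%.
- Non-VTE 1% (assumed): composite 3%; called better 96.8%.

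**5. An exact interval for VTE.** With a 1% baseline and n = 5000, the final lower limit exceeds 1% from 65 events (65/5000: 1.002% to 1.657%). The upper limit is below 2% up to 80 events (80/5000: 1.268% to 1.991%). Over three looks:

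- false finding of an increase at a true 1%: 2.5%
- false exclusion of a 1-point increase at a true 2%: 2.4%
- power to find an increase at a true 1.5%: 89%

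Both statements apply together at 65 to 80 events, about 63% of final looks at a true 1.5%. All of this depends on the baseline: if it were reconciled to 2%, a true VTE rate of 2% would be reported as increased only 2.4% of the time.

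**The case against.** The strongest reply is that this is a descriptive cohort whose aim is to estimate a frequency, that *better* is one bracketed word under the purpose of the interim analysis, and that the design works as intended. Much of this stands.

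- A reader might infer from the 96.8% at a true 3% that the rule is faulty. It is not: that figure is the design's intended power. The defect is in the name given to the result.
- A reader might infer that Section 8 has no decision threshold. An interval excluding 4% is clearly implied and reproduces the stated power; it only needs writing down.
- A reader might infer that a doubled VTE rate would usually pass as better. With the plan's own implied non-VTE share of 2%, this happens 2.4% of the time. The larger figures need a smaller, assumed share.
- The ambiguity of *complications* is minor. Section 8 also speaks of primary events, and its rates match Section 4. Section 6 does use the word for safety, "To evaluate the risk of bleeding-complications in patients having THA or TKA", so one clarifying phrase is worthwhile.
- Site additions in November 2012 and the enlarged sample suggest that early looks may already have been done. No look dates are given.

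What the reply does not remove is that the plan states a hypothesis, a power calculation, better and worse labels and adjusted interval levels, yet no section says what any result means for 1.2.

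**Conclusion.** The point holds as a defect of interpretation and decision rule, together with one sample size that disagrees with its own inputs. A composite interval below 4% supports only a rate below the stated maximum. Hypothesis 1.2 has no reference rate, margin or conclusion rule, and item 9 does not supply one. As written, 2076 is wrong for 1% against 2%: the named test needs 1143. Section 8's power figures and the 2838 are sound.

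Two stronger conclusions are not supported. The documents do not show that the composite would hide a doubling of VTE; that requires a non-VTE rate below the implied 2%. Nor would a VTE interval reliably flag a true 2% rate: that holds with a 1% baseline and fails with a 2% one.

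The conclusion rests on reading the Section 8 endpoint as the primary composite and its rule as an exact interval excluding 4%. This should be corrected, but it does not invalidate the design.

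**What to change.** - **Section 8.** Replace the better and worse labels with below and above the maximum rate. State that the rule is an exact interval for the primary composite excluding 4%.
- **Item 9.** Reconcile the baseline and N. If 1% against 2% was meant, restate N as 1143.
- **Hypothesis 1.2.** State which events count; Appendix 3 has a separate heading "Other thromboembolic events", so the term may reach beyond DVT and PE. Report an exact 95.2% interval for 90-day symptomatic VTE at the final analysis, and 99.5% or 99% intervals at any interim look not yet done. Compute the limits at the actual n, because item 6 takes the total above 5000.
- **Conclusions.** Report an increase if the lower limit exceeds the reconciled baseline. Report that an increase of 1 point or more is excluded if the upper limit is below baseline plus 1 point. State both when both apply. The 1 point comes from item 9 as a detectable difference, so its use as a margin needs its own justification.

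**Cost.** Wording and one more interval per analysis, with no extra patients or data. A plain claim of no increase is given up, and the two statements can apply together. Error is controlled per endpoint, not jointly: with the composite at exactly 4% and VTE at 1%, simulation put the chance of any false claim (composite below or above 4%, or VTE increased) at 6.9%. The VTE analysis must be marked post hoc for any look already done.
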